3.1. Study Population. We will recruit a total of 20 adult (≥ 18 years of age) men and women with severe COPD (forced expiratory volume (FEV1) $< 50\%$), who live in Monroe County (New York), have completed pulmonary rehabilitation for over 1 month, and have suffered from an AECOPD in the past year.

Number of Subjects:

We will enroll a total of 20 patients in our study who have completed pulmonary rehabilitation in Monroe County, New York.

Gender of Subjects: There are no restrictions on gender for this study with approximately 60% of subjects expected to be female.

Age of Subjects: All adults over the age of 18 will be included in the study with the average age of subjects enrolled expected to be around 65 years old.

Racial and ethnic origin: There are no restrictions on race/ethnicity for participation in the study. We anticipate enrollment demographics in the study will be similar to our clinic population, of which 85% of patients are white, 10% African American, and 5% from other groups.

Inclusion criteria: We will prospectively recruit a total of 20 adult (≥ 18 years of age) men and women with severe COPD (FEV1 $< 50\%$), who live in Monroe County, have completed pulmonary rehabilitation (over 1 month since completion), and have suffered from an AECOPD in the past year. Subjects must have standard sized windows in their bedroom and living room amenable to installation of the HEPAirX® device. All subjects must also expect to sleep each night of the 4 months (2 months of Period 1, and 2 months of period 2) in either their bedroom or living room for at least 6 hours/night, and not use other air filtering devices during the study.

[figure not shown]
Exclusion criteria: Exclusion criteria include subjects who are under age 18 and do not meet the inclusion criteria as defined above. Exclusion criteria include subjects under age 18, those who were smoking at the time of their prior COPD exacerbation, current smokers, those who live with an active smoker, homes with wood burning appliances, patients on chronic systemic corticosteroids (> 3 months continuous use in past 1 months), those who are planning to move in the next 12 months, those with an occupation that has a high pollutant exposure (e.g. professional drivers), those who already have a home air filtration device (other than basic furnace filter) and those who do not meet the inclusion criteria as defined above.

Vulnerable subjects: We do not plan to enroll vulnerable subjects.

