E.1. Study Population. We will recruit a total of 20 adult (≥ 18 years of age) men and women with severe COPD ($FEV1 < 50\%$), who live in Rochester, NY, have completed pulmonary rehabilitation, and have suffered from an AECOPD in the past year. **E.2. Health Outcomes.** Our primary endpoints will be the symptom score from the St. George's Respiratory Questionnaire (SGRQ; marker of functional status) described above in Section B.3 and the average daily count of steps taken using a Fitbit® brand wearable sensor (Aim 1). Our secondary endpoints are Plasma CRP measurements (Aim 2) and healthcare contacts for AECOPD (Aim 3). The subjects will wear the Fitbit® watch around their wrist during waking hours, which will automatically collect the daily count of steps and report this electronically to the research team via a secure account (Described below). The subjects will travel to the URMC lab at the specified time (described below) to have their plasma CRP drawn.

E.3. Study Protocol. We will conduct a randomized, blinded, crossover trial, where each of the 20 total subjects will be randomly assigned to **Group A** (Period 1 = 8 weeks of filtration/ventilation mode, 3 week washout period, Period 2 = 8 weeks of placebo mode [device runs but no filtration/ventilation]) or **Group B** (Period 1 = 8 weeks of placebo mode, 3 week washout period, Period 2 = 8 weeks of filtration/ventilation mode). Subjects will be blinded to which group they are randomly assigned, and only staff installing and monitoring the HEPAirX device and air pollution monitoring equipment, and not staff collecting or analyzing health outcomes, will know the assigned group. In the placebo mode of operation, the HEPAirX unit operates in exactly the same way (i.e. will look and sound the same), but it does not filter air to remove particles or have outdoor air exchanges to reduce gaseous pollutants. With 20 HEPAirX machines available and 2 required per subject, the timing of enrollment will be split into 2 groups of 10 patients (Two 19 week periods).

After getting informed consent from each study participant, we will schedule the 1st home visit within 2 weeks. Once consent to participate in the study has been obtained, we will provide subjects with:

- Five simple indoor air quality monitors which the subject will plug into an electrical outlet and set on a tabletop in a low traffic area of their living room and bedroom.

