E.4. Statistical Analysis. We will generate descriptive statistics for each subject, indoor air pollutant concentrations during each filtering/placebo mode session, and our main outcomes in Aim 1-Aim 3 (Aim 1: SGRQ symptom score and average daily step count; Aim 2: plasma level of CRP; Aim 3: number of healthcare encounters for AECOPD), comparing the change in each between the filtration and placebo groups. Given the crossover design, each subject will serve as their own control. Our statistical analyses are described below.

We will fit a random effects ANOVA model regressing the 8-week (Post-filtering SGRQ score (Aim 1) against the Pre-filtering SGRQ score, period ('Period 1' versus 'Period 2'), and filtering mode ('filter/ventilation mode' versus 'placebo mode'). If necessary, we will transform both post-filtering and pre-filtering SGRQ score to better satisfy model assumptions. Subjects will contribute two observations to the analysis and subjects will be included as random effects, recognizing correlations due to repeated measures on the same subject. Filtering mode will test whether the 'filtration/ventilation mode' produced a significant effect on subsequent SGRQ score than the 'placebo mode'. Next, the final survey 3 months after the 19 week intervention period concludes will be compared to survey 4 to explore the duration of observed changes. We expect that in view of the "washout period" between Period 1 and Period 2, there will be no carry-over of the effect of the intervention in Period 1 on the results for Period 2. Including period in the model allows us to assess the plausibility of this assumption. This same analysis used for Aim 1 will also be used for Aim 2, plasma CRP.

We will repeat the random effects ANOVA model, regressing the 8 week in Fitbit® measured average daily step count (Aim 1) (Post-filtering average daily step count) against the Pre-filtering average daily step count, period and filtering mode. Specifically the intervals selected for this analysis will be the week prior to Phase 1 compared to the final week of Phase 1 and the final week of the washout period compared with the final week of Phase 2. Indoor PM2.5 concentration will be analyzed similarly with the ANOVA model and will also use these same time intervals. We will repeat the random effects ANOVA model for average resting heart rate at the same time intervals.

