For Aim 3, the number of healthcare encounters for AECOPD, we will fit a Poisson regression of the number of COPD exacerbations in 8 weeks as a function of filtering mode (Filtering versus Placebo) and period. Should there be very few healthcare encounters, instead we will use a logistic regression to model whether there were any healthcare encounters. This model will allow us to evaluate the impact of filtering model on healthcare

encounters, while adjusting for period (e.g. Group A (Filtration followed by Placebo) or Group B (Placebo followed by Filtration) to determine if the order of intervention affected the outcome). Next we will compare healthcare encounters for AECOPD at the 3 month follow up period with Phase 2 outcomes in a similar way. Since this is a pilot study, power calculations are not provided, and effect estimates from the regression analyses described above will be used as preliminary data in an application for a larger, adequately powered R01 funded study.

Post hoc analyses:

1. Autonomic function: In addition to average resting heart rate, we will determine if the data are robust enough to calculate heart rate variability.
2. Genetic response: As mentioned, the stored blood may be used in a future analysis on the genetic response to air pollution related to respiratory outcomes
3. Particle Chemistry: The particles on the filters will be analyzed in the future for composition and potentially even included in cell exposure studies to determine the mechanistic impact of the pollutants.

SAFETY AND REPORTABLE EVENTS

Adverse Event Definition

An adverse event is any symptom, sign, illness, or experience, which develops or worsens during the course of the study, whether or not the event is considered related to study drug.

Serious Adverse Event

A serious adverse event is defined as any adverse medical experience that results in any of the following outcomes:

- death;
- is life-threatening;
- requires inpatient hospitalization or prolongation of existing hospitalization;
- results in persistent or significant disability/incapacity;
- is a congenital anomaly/birth defect; or
- requires medical or surgical intervention to prevent permanent impairment or damage.

Recording Adverse Events

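### Neither Aim 3 model, including the logistic fallback for sparse events, gives a finite effect estimate if one mode has no encounters, and the plan names no remedy

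*Combined protocol and SAP*

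**What the plan says.** Section 8, E.4 gives the main Aim 3 analysis as follows: "we will fit a Poisson regression of the number of COPD exacerbations in 8 weeks as a function of filtering mode", with period as the other term. The fallback comes next: "Should there be very few healthcare encounters, instead we will use a logistic regression to model whether there were any healthcare encounters".

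E.4 does not say how few encounters trigger the switch. It names no test or interval method and no penalised or exact version, and it has no rule for a mode without any encounter.

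The setting is small. Section 3.1 states "We will enroll a total of 20 patients in our study", and E.3 makes the trial a two-period crossover with 8 weeks in each mode. E.2 ranks the endpoint: "Our secondary endpoints are Plasma CRP measurements (Aim 2) and healthcare contacts for AECOPD (Aim 3"). On planning, E.4 says "Since this is a pilot study, power calculations are not provided" and assigns the regression estimates to the application for a larger, powered study.

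**The concern.** The fallback is there to rescue Aim 3 when encounters are scarce, which is when a mode is most likely to have none. Maximum-likelihood logistic regression cannot estimate the mode effect in that case, and the Poisson model it replaces cannot either. If filtration works well, an empty filtration cell becomes more likely, so the estimate can be lost when the data favour the device.

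At stake is a usable effect size with an interval, since E.4 treats the effect estimates as the trial's product for the next application. An infinite odds ratio cannot inform a sample size. With no test named, the same data could also be reported with very different p-values.

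**Working it through.** The documents give no Aim 3 power, event or p-value figure, so there is nothing of the plan's own to reproduce.

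**Inputs.** From the documents: 20 subjects (Section 3.1), each with 8 weeks in each mode (E.3), and terms for mode and period (E.4). E.4 says of the SGRQ model "Subjects will contribute two observations to the analysis"; I assume the same for Aim 3, giving 20 subject-periods per mode. Also assumed: a 10:10 split between Groups A and B, and all event rates. The only rate information is the entry criterion in Section 3.1, "have suffered from an AECOPD in the past year".

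**Why the fit fails.** At the maximum, the fitted number of filtration-mode events must equal the observed number. If that is zero, the fitted probability (or rate) must be zero, so the log-odds (or log rate) goes to minus infinity. This is a property of the likelihood, not a software fault.

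**Illustration.** Take 0 of 20 filtration and 6 of 20 placebo subject-periods with an encounter, one encounter each, placebo events split 3/3 by period.

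- Logistic, Wald: log-OR -22.7, SE 17,768, p = 0.999. The digits depend on where the software stops iterating; a second package gives -18.7, SE 2,405, p = 0.994.
- Logistic, likelihood ratio: deviance 33.817 - 24.435 = 9.382 on 1 df, p = 0.002. The profile 95% upper limit for the OR is 0.29. There is still no finite point estimate.
- Poisson: Wald p = 0.999; likelihood ratio 22.765 - 14.448 = 8.317 (8.318 before rounding), p = 0.004.

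**How often filtration mode alone has no events.** Assume independent Poisson counts. With μ = rate × 20 × 8/52 and rate ratio RR, the chance is exp(-μ·RR) × (1 - exp(-μ)).

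| Placebo rate per patient-year | μ | RR 0.5 | RR 1 |
|---|---|---|---|
| 0.5 | 1.54 | 0.463 × 0.785 = 36% | 0.215 × 0.785 = 17% |
| 1 | 3.08 | 0.215 × 0.954 = 20% | 0.046 × 0.954 = 4% |
| 2 | 6.15 | 0.046 × 0.998 = 5% | 0.2% |
| 3 | 9.23 | 0.0099 × 1.000 = 1% | 0.01% |

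Adding the case where only placebo mode is empty, the chance that exactly one mode has no events at RR 0.5 is 48%, 24%, 5% and 1%.

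**Same data, methods that tolerate a zero.**

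- Firth-penalised logistic (mode + period): OR 0.058, 95% profile CI 0.0004 to 0.54, p = 0.008. A 2/4 or 4/2 split by period gives OR 0.054, CI 0.0004 to 0.52, p = 0.008.
- Exact McNemar: no subject has a filtration encounter, so all 6 are discordant in one direction. p = 2 × 0.5^6 = 0.031. The 95% upper limit for the discordant proportion is 1 - 0.025^(1/6) = 0.459, so the conditional OR is below 0.459/0.541 = 0.85.

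**The case against.** Two stronger readings are tempting, and the documents support neither. A reader might infer that a 0 versus 6 result would be reported as p = 0.999 with no usable interval. That needs a Wald test, and E.4 names no test: the likelihood-ratio test from the same fit gives p = 0.002 and a one-sided bound. A reader might also infer that switching to logistic regression causes the failure, so that dropping the fallback would cure it. The planned Poisson model fails in the same way, so the cure is the estimation method.

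The case against goes further. The 0 versus 6 split is invented, 0 versus 7 would be clearer still (exact p = 2 × 0.5^7 = 0.016), and with the trigger undefined nothing shows that six encounters would invoke the fallback. All rates are assumed. Because entry requires a recent exacerbation, rates of 2 or 3 per year are plausible, and there the risk is 5% or less. Aim 3 is secondary in an unpowered pilot, and E.4 also promises descriptive statistics for it, so raw counts would survive.

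The any-encounter outcome also has a merit: it is not inflated when one patient has several encounters. A Poisson or exact binomial analysis of counts treats repeats as independent. In a simulation with no effect and strong assumed clustering (gamma shape 0.25 within subject-periods), the exact binomial test had type I error of 12% at 2 per year and 18% at 3. This is a good reason to keep the fallback outcome.

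All of this limits the size of the point. What remains is that neither named model gives a finite estimate with an empty mode, and the plan offers no alternative.

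**Conclusion.** The concern holds as a gap in method. If one mode has no encounters, both Aim 3 models lack a finite estimate, Wald output is meaningless, and the choice between Wald and likelihood-ratio p-values (0.999 or 0.002 in the example) is left open. The failure itself is mathematical and needs no assumption. How often it would occur rests on assumed rates and independent Poisson counts: with a halved rate, filtration mode alone is empty with probability from about 36% at 0.5 per patient-year to 1% at 3. The trial's primary conclusions are untouched; what is at risk is the Aim 3 estimate passed to the larger study. The change is worth making because it is cheap.

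**What to change.** In E.4, keep the any-encounter fallback but specify:

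1. Logistic regression on mode and Period 1/2 with Firth's penalty, reporting the odds ratio with a profile-likelihood interval and penalised likelihood-ratio p-value.
2. An exact McNemar comparison of the two modes within subjects alongside it. The two complement each other: the Firth model adjusts for period but, as specified, not for pairing, while McNemar uses the pairing but not period.
3. A trigger fixed in advance, for example whenever either mode has fewer than 5 subjects with an encounter.

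**Cost.** A few sentences and standard software. The penalised estimate is shrunk and less familiar, the exact test is conservative, and repeat encounters are not counted in the fallback.

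The example trigger would be met often. Let q = 1 - exp(-rate × 8/52) be the chance that a subject has an encounter in a mode, with the number of such subjects binomial (20, q) and the modes independent. At a halved rate, the chance that at least one mode has fewer than 5 is above 99% at placebo rates of 0.5 or 1 per year, about 91% at 2 and 64% at 3. The team should expect this to be the working Aim 3 analysis, or choose a lower threshold knowingly. If the Poisson model is used with an empty mode under another trigger, it needs the same penalty.

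### The Aim 3 text explains its period covariate as Group A or Group B, which is treatment sequence; if coded that way, the filter rate ratio is not adjusted for period

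*Combined protocol and SAP*

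**What the plan says.** All references are to the combined protocol and SAP.

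- **Section 8, E.4, Aim 3, model sentence.** The number of exacerbations in 8 weeks is modelled by Poisson regression "as a function of filtering mode (Filtering versus Placebo) and period". A logistic model for any encounter replaces it if encounters are very few.
- **Section 8, E.4, Aim 3, explanation of the model.** The text speaks of "adjusting for period (e.g. Group A (Filtration followed by Placebo) or Group B (Placebo followed by Filtration", with the stated purpose "to determine if the order of intervention affected the outcome".
- **Section 8, E.4, Aim 1 (also used for Aim 2).** The covariates after the pre-filtering score are "period ('Period 1' versus 'Period 2'), and filtering mode".
- **Section 5, E.3.** Group A is "Period 1 = 8 weeks of filtration/ventilation mode, 3 week washout period, Period 2 = 8 weeks of placebo mode"; Group B is "Period 1 = 8 weeks of placebo mode, 3 week washout period, Period 2 = 8 weeks of filtration/ventilation mode". Group is therefore fixed for each subject. E.3 says that the 20 subjects are randomised but gives no ratio or blocking.

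**The concern.** Within one section, the same word stands for two different variables. Period 1 versus Period 2 varies within a subject; Group A versus Group B does not. The bracket also comes with a purpose, testing order, that fits sequence, so a programmer could reasonably code Group.

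The adjustment would then fail to do its job. The two periods start 11 weeks apart (8 weeks plus a 3-week washout), so exacerbation risk may differ between them. If the sequences are unequal in size, or Period 2 counts are lost unevenly, that difference enters the filter rate ratio. Aim 3 would also be analysed differently from Aims 1 and 2 without anyone having chosen to do so. The estimate matters because E.4 intends the regression estimates as preliminary data for a larger trial.

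**Working it through.** The plan gives no event rate, effect size or power for Aim 3, so there is no figure of its own to reproduce. The check is on the design.

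**Inputs from the documents:** 20 subjects, two sequences, and one filter and one placebo 8-week count per subject.

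**Assumptions:** Period 2/Period 1 rate ratio r = 1.5 or 2 (and the reverse), common to both enrolment waves; unequal splits of 12/8 and 13/7; three subjects of one sequence without a Period 2 count; true filter rate ratio 1 unless stated.

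**1. Group carries no period information.** Over the four sequence-by-period cells, the Group and Period indicators have correlation 0. Period is the mode-by-sequence interaction: the matrix [1, mode, Group] has rank 3, and adding Period raises it to 4.

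**2. Complete data: mode + Group equals mode alone.** Let a and b be the fitted placebo rates in Groups A and B, and R the filter rate ratio. Fitted placebo events total nA·a + nB·b, and fitted filter events total R(nA·a + nB·b). Poisson fitting matches both totals to the observed ones, so R = filter events / placebo events, which is the unadjusted ratio. In 300 simulated 12/8 trials the two log rate ratios differed by at most about 4 × 10⁻¹⁴.

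**3. Size with complete data.** Group A has the filter in Period 1 and Group B in Period 2, so with no filter effect

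R = (nA + nB·r) / (nA·r + nB).

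| Split A/B | r = 1.5 | r = 2 | Period 1/2 coding |
|---|---|---|---|
| 10/10 | 25/25 = 1.000 | 30/30 = 1.000 | 1.000 |
| 12/8 | 24/26 = 0.923 | 28/32 = 0.875 | 1.000 |
| 13/7 | 23.5/26.5 = 0.887 | 27/33 = 0.818 | 1.000 |

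Reversing either the imbalance or the period effect gives the reciprocal: at 8/12 and r = 2, (8 + 24)/(16 + 12) = 32/28 = 1.143. A true ratio of 0.7 is multiplied by the same factor: at 12/8 it becomes 0.646 (r = 1.5) or 0.612 (r = 2), against 0.700 with period coding.

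**4. Missing Period 2 counts.** Start at 10/10 with three Group A counts missing in Period 2, and r = 2. Taking the Period 1 rate as 1, expected events are A-filter 10, A-placebo 14, B-placebo 10 and B-filter 20, on 10, 7, 10 and 10 subject-periods.

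- Mode alone: (30/20)/(24/17) = 1.0625.
- Mode + Group: solve 24·10R/(10R + 7) + 30·R/(R + 1) = 30. At R = 1.069 the left side is 14.50 + 15.50 = 30.00, so R = 1.069.
- Mode + Period 1/2: 1.000.

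With r = 1.5, Group coding gives 1.040. Here Group coding no longer equals mode alone, but it still does not remove the period effect.

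**5. Logistic fallback.** At 12/8, with an assumed 20% chance of any encounter in Period 1 and twofold odds in Period 2, the filter odds ratio is 0.872 with or without Group and 1.000 with Period 1/2.

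**6. How likely is imbalance?** If allocation is simple (not stated), P(10/10) = 184,756/1,048,576 = 0.18 and P(12/8 or worse) = 1 − (184,756 + 2 × 167,960)/1,048,576 = 0.50.

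**7. Against sampling error.** Assume 1 to 3 exacerbations per subject-year. Then 20 × 8/52 × (1 to 3) gives about 3 to 9 events per mode, and the standard error of the log rate ratio, √(2/events), is about 0.8 to 0.5. The 12/8 bias at r = 2 is |ln 0.875| = 0.13, roughly 0.2 to 0.3 standard errors.

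**The case against.** The strongest reply is that the model is specified correctly. The model sentence lists filtering mode and period, E.3 names Periods 1 and 2, and the Aim 1 paragraph defines the covariate. The bracket comes later, in a description of what the model allows, and opens with an e.g. A reader might infer that the plan commits Aim 3 to the wrong covariate. The documents do not go that far; the intent may have been right and the gloss loose. What stands is that the only explanation of period given for Aim 3 names a different variable and attaches a matching purpose, and nothing else settles the coding.

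Secondly, bias needs several conditions together: the bracket is followed, sequences are unequal or loss is uneven, and there is a period effect. That is correct. The last need not be common to both waves. Devices suffice for ten subjects at a time, so the waves run at different calendar times and a seasonal effect could reverse. If rates go from 1 to 2 in one wave and from 2 to 1 in the other, with 6/4 in each, the ratio is (14 + 16)/(16 + 14) = 1.00.

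Thirdly, withdrawal need not lose the Aim 3 count, since Section 6 says that exacerbations come from existing medical records. This stands: the missing-data case is conditional. It also limits the claim that Group coding amounts to no adjustment at all, which is exact only with complete data.

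Finally, E.3 uses both words again for enrolment, "split into 2 groups of 10 patients (Two 19 week periods". A reader might count this as a third definition of the covariate. It describes scheduling and is not a model term, so renaming it would change no result.

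**Conclusion.** The point holds as a conflict in the text with a conditional consequence. Coded as the bracket describes, the Aim 3 model would not adjust the filter rate ratio for period. Coded as Period 1 versus Period 2, it returns the true ratio in every scenario tried.

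The consequence is modest. It is nil at 10/10 with complete data and moderate under the assumed imbalances or losses and a period effect shared by both waves. It is probably well inside the sampling error of a secondary endpoint with few events. The documents supply neither the period effect nor the allocation method, so these sizes illustrate the problem and do not predict it. They do not support a statement that the Aim 3 result will be biased. The reason to act is that the rule as explained does not do its stated job, and correcting it is free.

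**What to change.** In E.4, replace the Group A/Group B bracket in the Aim 3 text with: *period (Period 1 versus Period 2), coded as in the Aim 1 model*. State that the same coding applies to the logistic fallback. If the order of intervention is of interest, list Group as a separate, descriptive term in addition to period.

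Cost: one sentence in E.4, with no change to data collection, visits or procedures.
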